7.1. Study Outcomes

Primary outcomes: feasibility and acceptability.

Feasibility: Key metrics will include the number of screened, eligible, consented and randomized participants; retention rates; session attendance; and individual mindfulness practice. We will consider either condition feasible under the following conditions:

- 1) If we achieve retention rates of 80% at the final follow-up visit
- 2) If patients attend at least 70% of the planned sessions
- 3) If patients report to have completed 70% of the assigned individual home practice exercises
- 4) Intervention session calls lasting approximately 20 minutes
- 5) Fewer than three rescheduled intervention calls

Acceptability: We will assess the following domains:

- 1) Participants' experience in the study (qualitative data collection)

- 2) Participants' ratings of the interventions on a satisfaction survey. The intervention will be considered acceptable if ≥80% of participants responds that they are at least somewhat satisfied with the intervention.

Secondary outcomes:

Preliminary estimates of effect size of mindfulness training vs. attention control on changes from baseline ART adherence, risky sex behaviors as well as on hypothesized mediators (i.e., mindfulness, depression, perceived stress, and impulsivity) will be assessed. We expect that the mindfulness training condition will achieve larger positive changes in ART adherence and risky sexual behaviors compared to the attention control condition.

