8. STUDY ASSESSMENTS

Overview

Table 8.2 provides the schedule of study assessments for this pilot RCT. All assessments will be conducted in-person. The PD will be responsible for data collection; see section 7.6 for blinding consideration. Because not all participants can be reached for assessments on their due date, windows have been established to determine when to record a protocol violation or consider assessments missing (Table 8.1).

Table 8.1

Assessment	Window
Baseline	Within 60 days from screening visit
Post-Intervention	Within 2 weeks of final intervention session
Follow-up	12 weeks (+/- 2) after completing final intervention session

All visits will be conducted at the Immunology Center (described earlier).

Table 8.2 Schedule of Study Assessments

Assessment	S	BL	At each session	Post	FU
Screening					
HIV infection status	X				
ART adherence	X				
Viral load	X				
Psychological distress	X				
Sexual risk behavior (past 3 months)	X				
Prior mind-body training	X				
Hearing impairment	X				
Suicidal ideation	X				
Telephone Access	X				
Literacy	X				
Feasibility and Acceptability					
n of screened individuals		X			
n eligible		X			
n enrolled		X			
n refusing to participate		X			
Reasons for refusing participation		X			
n of dropouts and lost to follow-up			X	X	X
Reason(s) for dropping out			X	X	X
Sessions attendance (both conditions)			X		
Individual home practice (both conditions)			X	X	X
Acceptability Survey/ Satisfaction scale				X	X
Qualitative Interview				X	X
Efficacy					

ART adherence: self-reported measure		X		X	X
ART adherence: objective measure (unannounced pill count)		X*		X	X
Viral load (ART adherence biomarker)		X		X	X
Sexual risk: Self-report		X		X	X
STI (sexual risk biomarker)		X			X
Mediators					
Mindfulness		X		X	X
Depression		X		x	X
Anxiety		X		X	X
Perceived stress		X		x	X
Impulsivity		X		x	x
Moderators and Descriptors					
Demographic characteristics		X			
Perceived physical health		X		X	X
Medical history; medications		X			X
Social support		X			
Sleep		X		X	X
Alcohol use		X		X	X
Other Drug Use		X		X	X
Smoking		X		X	X
Nutrition/Eating		X		X	X
Food Security		X		X	X

S = screening; BL = baseline; post = post-intervention; FU = follow-up. * Scheduled within one week of the baseline.

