8.4. Post-Intervention and Follow-up Assessments

Two additional assessments will take place (a) post-intervention (within two weeks of finishing the program) and (b) at 3 months post-intervention (within 12 weeks (+/- 2 weeks) after finishing the program):

- Feasibility
 - Retention rates; drop-out counts and reason for dropping out will be maintained by the RA.
 - Adherence to Mindfulness Training and Health Coaching
 - Session attendance will be recorded at each session by the instructor using an attendance log.
 - Individual practice at home will be self-reported during each session.
- Acceptability
 - Satisfaction Survey¹⁷⁸ reporting how informative, interesting, and helpful the MT was; how likely they are to continue practicing after the training; whether they would recommend it to other PLWH; and whether they have suggestions for how we might improve it. Participants will rate the interventions on a scale from 0 to 6.
- Qualitative data collection
 - At each assessment, participants will be asked to participate in an interview to solicit information about their experiences. They will be asked open-ended questions about their experiences. The semi-structured qualitative interview guide can be found in Appendix 4.
- Efficacy (measures described at Baseline)
 - Adherence to ART
 - Self-reported adherence
 - Unannounced pill counts
 - Viral Load
 - Sexual Risk
 - Self-report of risk behavior
 - STI (chart diagnosis)
 - STI (lab-diagnosed)
- Moderators (measures described at Baseline)
 - Perceived health
 - Sleep
 - Alcohol Use
 - Substance Use
 - Smoking
- Mediators (measures described at Baseline)
 - Mindfulness

- Depression
- Perceived stress
- Impulsivity
- Anxiety

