12.2. Primary Outcomes: Feasibility and Acceptability

Because this is a pilot study, analyses are not powered to detect treatment effects nor to formally test mediation or moderation. Any formal statistical testing will be only exploratory.

Feasibility. To determine feasibility of conducting a RCT, we will calculate the percentage of individuals who were: eligible; consented; accepted randomization; and returned for the post-intervention and 3-month follow-up. Based on our recent trials (R01-MH068171), we expect $\geq 80\%$ of all patients to return for the 3-month follow-up and will conclude the intervention is feasible if the follow-up rate is at least 80%. To determine feasibility of the MT and AC interventions, we will calculate the percentage of individuals who attended their intervention sessions. Based on previous research, we predict that $\geq 70\%$ of those assigned to a MT will complete all intervention sessions.

Acceptability. To determine the acceptability of the interventions, we will calculate means for the satisfaction surveys, and inspect responses. The intervention will be considered acceptable if $\geq 80\%$ of participants respond that they are satisfied with the intervention. We will also collect metrics (e.g., duration of calls, number of cancelled sessions). We will construe as evidence of acceptability, patients completing all ≥ 7 sessions, with call durations averaging 20 minutes per call, and with fewer than 3 rescheduled sessions.

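### The 80% acceptability rule defines success differently in sections 7.1 and 12.2, and neither definition is tied to a score on the 0–6 satisfaction survey

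*Combined protocol and SAP*

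**What the plan says.** Section 7.1 gives the status of the outcome: "Primary outcomes: feasibility and acceptability". Its numeric acceptability criterion is met if at least 80% "of participants responds that they are at least somewhat satisfied with the intervention".

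Section 12.2 repeats the criterion with the same 80% mark but counts the share "of participants respond that they are satisfied with the intervention". For the survey itself it plans that "we will calculate means for the satisfaction surveys, and inspect responses".

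Section 8.4 describes the survey as "reporting how informative, interesting, and helpful the MT was", followed by intention to keep practising, willingness to recommend it and suggestions for improvement. On the response format it says: "Participants will rate the interventions on a scale from 0 to 6". It gives no labels for the scale points and no cut-off. In Table 8.2 the row "Acceptability Survey/ Satisfaction scale" is marked at both the post-intervention and the follow-up visit.

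**The concern.** Both sentences are current text and both are decision rules for a primary outcome. Section 12.2 declares all formal testing exploratory, so fixed criteria such as this one are how the trial reaches its primary conclusions.

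The two rules share a threshold but not a definition of who counts towards it. Someone who is only somewhat satisfied is a success in 7.1. In 12.2 that person may or may not be one. Nothing in the documents says which section governs, and nothing translates either wording into a score from 0 to 6. An analyst holding the completed surveys would have to choose a cut-off after seeing the ratings, and the choice could settle the result.

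**Working it through.** There is no figure in the plan to reproduce. Section 12.6 bases the sample size on practical considerations, and no power or precision calculation is given for acceptability.

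**Inputs from the documents**
- Pass mark: at least 80% (7.1 and 12.2).
- Arm size: 25 (12.6).
- Survey scale: 0 to 6 (8.4).
- Retention target: 80% at final follow-up (7.1). This is 0.80 × 25 = 20 per arm and is used here only as a plausible number of returned surveys.

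**The rule as a count.** The number needed is 0.80 × n: 20 of 25, or 16 of 20. One participant is 1/25 = 4 percentage points of a full arm.

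**Step 1: the two wordings on one set of answers.** Assume 20 surveys in an arm: 12 satisfied, 4 only somewhat satisfied, 4 neither.
- Section 7.1: (12 + 4)/20 = 80%, acceptable.
- Section 12.2, read strictly: 12/20 = 60%, not acceptable.

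**Step 2: the missing cut-off.** Assume 25 ratings, with scores 1, 2, 3, 4, 5, 6 given by 1, 1, 2, 4, 9, 8 participants.

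| Score counted as success | Successes | Percentage | Result |
|---|---|---|---|
| 3 or more | 23/25 | 92% | pass |
| 4 or more | 21/25 | 84% | pass |
| 5 or more | 17/25 | 68% | fail |
| 6 only | 8/25 | 32% | fail |

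**Step 3: why the planned mean does not help.** The mean of those ratings is (1 + 2 + 6 + 16 + 45 + 48)/25 = 118/25 = 4.72. A second set, with 23 scores of 5, one of 2 and one of 1, has the same mean: (115 + 2 + 1)/25 = 4.72. At a cut-off of 5 or more, the first set gives 17/25 = 68% (fail) and the second 23/25 = 92% (pass). The mean does not determine the percentage.

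**Step 4: how often the two wordings could disagree.** Let q be the true share satisfied and s the further share only somewhat satisfied. With X binomial on n = 25, the chance of passing is P(X ≥ 20), using probability q + s under 7.1 and q under a strict 12.2. Anyone who passes the strict definition also passes the lenient one, so the chance of opposite results is the difference between the two.

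| Assumed q | Assumed s | Pass under 7.1 | Pass under strict 12.2 | Opposite results |
|---|---|---|---|---|
| 70% | 20% | 96.7% | 19.3% | 77% |
| 70% | 10% | 61.7% | 19.3% | 42% |
| 80% | 10% | 96.7% | 61.7% | 35% |

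The splits in steps 1 to 4 are all assumptions. The documents give no expected ratings.

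**The case against.** The strongest reply is that 12.2 is shorthand for 7.1. It keeps the same threshold in nearly the same sentence, and without printed response labels it cannot be shown that satisfied is a separate, stricter category. This stands as a possibility. It does not remove the problem, because the shared rule would still have no score attached on the 0–6 scale, and step 2 shows that the score can decide the result.

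It can also be said that acceptability rests on more than this percentage. Section 7.1 adds qualitative data, and 12.2 adds session completion, call length and rescheduling. That is correct and limits the consequence, but the 80% sentence is written in both places as a rule in its own right.

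Four stronger readings are tempting, and the documents do not support them.
- *A respondents-only percentage.* Both sections refer to a share of participants. Section 6.3 keeps people withdrawn from the intervention in assessment, and 12.7 provides for following up withdrawals. What is missing is a statement of how an absent survey counts.
- *A survey for the mindfulness arm only.* The content list in 8.4 mentions only that arm, but the same item goes on to say that the interventions, in the plural, are rated.
- *No overall satisfaction question.* Section 8.4 summarises the survey and cites a general client-satisfaction scale; the questionnaire itself is not among the appendices. The summary cannot show that the item is absent.
- *This percentage alone decides progression to the R01 trial.* Section 2.2 envisions that trial after the pilot, and Appendix 4 says the interviews will inform refinements. Neither makes this figure a gate.

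**Conclusion.** The inconsistency is real and should be removed before ratings are examined. One primary-outcome threshold carries two success definitions, neither is linked to the survey scale, and the planned summary by means cannot supply the percentage. The result can then depend on which section is followed: 80% against 60% in the 20-person illustration, and opposite results in 35% to 77% of trials across the three assumed splits.

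Those sizes rest entirely on assumed ratings and on the two wordings corresponding to different scores, which is likely but not shown. If they mean the same thing, the conflict between sections disappears and the undefined cut-off remains.

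**What to change.** - Put one identical rule in 7.1 and 12.2.
- Before any ratings are examined, name the survey item that is used, the same for both arms, and the 0–6 score that counts as success. If the 7.1 rule is kept, this is the score corresponding to somewhat satisfied.
- In 12.2, add the percentage at that cut-off, by arm, beside the planned means.
- State whether the post-intervention or the follow-up survey decides.
- State how missing surveys are handled, and report the percentage both over respondents and over all randomised participants. In the 20-person illustration under 7.1, these are 16/20 = 80% and 16/25 = 64%.

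Non-respondents need not be counted as not satisfied in the deciding figure. If 20 of 25 surveys in an arm were returned, that convention would require all 20 respondents to be satisfied (20/25 = 80%), and it would count retention a second time, since 7.1 already has a separate retention criterion. Which figure decides is for the sponsor to choose, provided it is fixed in advance.

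The cost is a few sentences in 7.1, 8.4 and 12.2. No visit or participant is added. The sponsor gives up only the freedom to choose the cut-off after the ratings are known.

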7.2. Design Overview

Participants ($n = 50$; 25 per condition) will be assessed (i.e., baseline), randomized to intervention (i.e., 8 weekly phone-delivered sessions of mindfulness training or the attention control intervention), and reassessed at the end of the intervention (i.e., post-intervention), and at 3 month post-intervention follow-up.

7.3. Study Interventions

Intervention setting. Intervention sessions for both conditions will be individually delivered over the phone. Prior to the beginning of the intervention instructors will contact participants to set up the best time to deliver the intervention.

Session frequency. Participants in both conditions will receive a 30-minute phone call session once a week for 8 weeks.

Mindfulness training (MT). The intervention protocol is based on the MT protocol pilot-tested in our preliminary work¹²⁰ (see Appendix 1 for a script of each session). This intervention maintains the basic components of Mindfulness Based Stress Reduction (MBSR)⁷⁵ but has been streamlined to distill the active ingredients for phone delivery. The MT intervention involves training in the following practices: (1) Awareness of breath, a technique in which trainees learn to attend to the sensations associated with breathing; and (2) Body scan, a technique based on the cultivation of attention to bodily sensations that would normally go unnoticed. Later, participants are gradually trained to (3) direct their attention to simple activities of daily life and (4) to become aware of their own thoughts and emotions. Only at the final session they (5) practice “open awareness” – a technique by which the participant is invited to direct his/her attention to any event arising in their field of experience at a given moment, whatever it may be, e.g., a physical sensation, sound, emotion, or thought.

Individual home practice. In addition to the weekly training session, participants will practice mindfulness techniques for 15 minutes daily on their own with the guidance of a digitally recorded, standardized guided mindfulness practice containing the techniques learned with the instructor. The mindfulness practice digital recording will be provided in different formats (CD or MP3 file) depending on the participant's preference. (Please see Appendix 1 for a detailed script of the CD/MP3 recording).

MT instructors. MT instructors will be graduates from the teachers' training program at the University of Massachusetts Center for Mindfulness with ≥ 5 years teaching experience. To ensure consistency of delivery, each patient will be trained by the same instructor throughout the intervention. Instructors will receive 3-hour training session in the delivery of the MT intervention, self-recording and fidelity checks, protocols, and reporting. Supervision will be

provided during regular conference calls. These calls will be scheduled weekly during the first month, biweekly during the second month, and monthly thereafter. Additional ad hoc calls will be scheduled if needed. The calls will be led by [name], and will involve discussion of issues that arise during MT sessions.

Attention control (AC) condition. The AC condition is an active, structurally equivalent, intervention to control for the time and attention received in the MT condition. The content of the AC intervention was developed using participants' feedback from the Study 1-3 focus groups and will include health topics suggested by the focus groups including: Sleep, Nutrition, Sun Safety, Physical Activity, and Home and Travel Safety (see Appendix 2 for a script of each session).

Individual home practice. Each health topic has an associated daily practice activity to control for the time patients in the MT intervention spend practicing mindfulness exercises on their own (15 minutes daily). (See Appendix 2 for an explanation of daily practice for the AC condition).

AC instructors. Instructors will be clinical psychology residents with ≥ 5 years of experience. To ensure consistency of delivery, each patient will be trained by the same instructor throughout the intervention. Instructors will receive undergo training in the delivery of the general health intervention. Supervision will be provided during regular conference calls. These calls will be scheduled weekly during the first month, biweekly during the second month, and monthly thereafter. Additional ad hoc calls will be scheduled if needed. The calls will be led by [name], and will involve discussion of issues that arise during AC sessions.

7.4. Concomitant Interventions

Allowed Interventions: Participants are allowed to continue ALL the medications and follow all behavioral recommendations prescribed by their care providers. We will monitor all medications used and control for these in data analyses.

Prohibited Interventions: Yoga, stress reduction, or other mind-body training.

7.5. Treatment Fidelity

To ensure that interventions are delivered with fidelity, we will have developed, a protocol, manual, and script of each session. The script will not be used verbatim but instructors will be trained to follow the sequence indicated in the Session Guides. As noted earlier, to avoid contamination, different instructors will deliver the MT and AC interventions. Assessments of treatment fidelity will be conducted following the guidelines developed by the Treatment Fidelity Workgroup.^{121,122} We will create checklists of essential intervention components for the MT and AC. At the end of each session instructors will complete the auditor checklist corresponding to that session. Instructors will also digitally record each session. We will audit 10% of all recordings using the checklist to ensure that the interventions are being delivered as intended.

7.6. Blinding

This is a phase 2 pilot study testing the feasibility of a behavioral intervention; participants will not be blinded.

Blinded personnel:

- Principal Investigators and all Co-Investigators
- Data management and data analysis personnel
- MT and AC instructors will be blinded to the study outcomes.

Non-blinded personnel:

- Project Director. Blinding the PD would be impractical given that she will be randomizing the patients to either condition. The impact of un-blinding the PD will be minimal because study

surveys are completed electronically by participants and the PD will NOT be involved in data analysis.

8. STUDY ASSESSMENTS

Overview

Table 8.2 provides the schedule of study assessments for this pilot RCT. All assessments will be conducted in-person. The PD will be responsible for data collection; see section 7.6 for blinding consideration. Because not all participants can be reached for assessments on their due date, windows have been established to determine when to record a protocol violation or consider assessments missing (Table 8.1).

Table 8.1

Assessment	Window
Baseline	Within 60 days from screening visit
Post-Intervention	Within 2 weeks of final intervention session
Follow-up	12 weeks (+/- 2) after completing final intervention session

All visits will be conducted at the Immunology Center (described earlier).

Table 8.2 Schedule of Study Assessments

Assessment	S	BL	At each session	Post	FU
Screening					
HIV infection status	X				
ART adherence	X				
Viral load	X				
Psychological distress	X				
Sexual risk behavior (past 3 months)	X				
Prior mind-body training	X				
Hearing impairment	X				
Suicidal ideation	X				
Telephone Access	X				
Literacy	X				
Feasibility and Acceptability					
n of screened individuals		X			
n eligible		X			
n enrolled		X			
n refusing to participate		X			
Reasons for refusing participation		X			
n of dropouts and lost to follow-up			X	X	X
Reason(s) for dropping out			X	X	X
Sessions attendance (both conditions)			X		
Individual home practice (both conditions)			X	X	X
Acceptability Survey/ Satisfaction scale				X	X
Qualitative Interview				X	X
Efficacy					

ART adherence: self-reported measure		X		X	X
ART adherence: objective measure (unannounced pill count)		X*		X	X
Viral load (ART adherence biomarker)		X		X	X
Sexual risk: Self-report		X		X	X
STI (sexual risk biomarker)		X			X
Mediators					
Mindfulness		X		X	X
Depression		X		x	X
Anxiety		X		X	X
Perceived stress		X		x	X
Impulsivity		X		x	x
Moderators and Descriptors					
Demographic characteristics		X			
Perceived physical health		X		X	X
Medical history; medications		X			X
Social support		X			
Sleep		X		X	X
Alcohol use		X		X	X
Other Drug Use		X		X	X
Smoking		X		X	X
Nutrition/Eating		X		X	X
Food Security		X		X	X

S = screening; BL = baseline; post = post-intervention; FU = follow-up. * Scheduled within one week of the baseline.

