6.3. Retention Plan

Patients will be asked to provide two different telephone numbers (home and mobile phone number) and an email address. Participants will be asked to provide contact information for two locators to be used in the event that contact is lost with the participant. Locators will not be given information about the nature of the research study. The study tracking system will identify participants due for a visit. We will send mail/email reminders or phone messages to remind patients of their follow-up appointments. Participants who wish to drop out of the study will be queried as to their reasons for doing so and every attempt will be made to address their concerns. In addition, we will provide monetary compensation to patients for their time and expenses. Participants will receive \$40 cash for the baseline assessment, \$40 cash for the post-intervention assessment, \$50 cash for the follow-up assessment and \$10 cash each for the pill count telephone calls (seven total) for a total of \$200.

If a participant does not complete all of the baseline procedures (including the two pill counts) within 60 days of enrollment, then he or she will be considered lost to follow-up.

If a participant does not complete two intervention weeks in a row he or she may be withdrawn from the intervention portion of the study per PD and PI discretion. These participants would still be contacted for pill count assessments and follow-up assessments.

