Please note that retention, attendance are feasibility outcomes; consequently dropouts, missing session, and missing self-reported practice will not be considered protocol deviations. This information will be collected and monitored (as aggregate data and without breaking the PI blind status).

Protocol amendments. Please also note that given the pilot nature of this study, we may need to amend the original protocol in response to feasibility issues (e.g., if we realize that our eligibility criteria are too strict, unnecessary and negatively affect recruitment). If needed, we will submit an amended protocol to NCCIH for approval in the following cases: any change that may affect patient safety (e.g., change in eligibility criteria; change in risk, regardless of whether risk is increased or decreased); any change that changes scientific intent or study design, or affects human subject protection; addition/deletion of a site; addition/deletion of key study personnel; change of institution for key study personnel; change in enrollment targets. Amendments will also be submitted to the IRB in accordance with IRB policies at TMH.

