12.7. Missing Data

As noted earlier, the primary analysis will be performed according to the intention to treat approach. Withdrawals will be asked to complete follow-up assessments and home visits or phone interviews will be arranged if necessary. If we encounter substantial missing data, possible options will include using accepted statistical methods (e.g., use of complete data only, use of multiple imputation, use of modified weights and model-based procedures).

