- Participant encouraged to practice AOB exercise during the following week with aid of study CD - track 1 once a day; confirm next meeting

Session 2: AOB/Attention to Daily Experience

- Questions and answers related to practice in previous week (10')
Ask family member to get small raisin box (provided)
- Exercise: direct the attention to the bodily sensations associated with breathing (AOB) (10')
- Attention to daily experience: exercise of paying attention to everyday activity (eating a raisin) (5')
- Feedback from participant (5')
- Participant encouraged to practice AOB exercise during the following week with aid of study CD - track 1 once a day; confirm next meeting

Session 3: AOB/BodyScan

- Questions and answers related to practice in previous week (10')
- Body scan exercise: participant is invited to sit in comfortable chair. (10')
Participant is instructed to move his/her awareness to different parts of the body in a systematic way, beginning with the toes and progressing to the top of the head, noticing whatever sensations happen to be present in that part of the body at that moment. End with short AOB exercise.
- Feedback from participant (10')
- Participant encouraged to practice Body Scan exercise during the following week with aid of study CD - track 2 once a day; confirm next meeting

Session 4: AOB/Body Scan/Attention to Daily Experience

- Questions and answers related to practice in previous week (10')
Ask relative to get a glass of water or other non-alcoholic drink that participant likes
- Short AOB exercise, followed by Body Scan exercise (10')
- Attention to daily experience: drinking exercise. (5')
- Feedback from participant (5')

Mindfulness Training for PLWH

- Participant is instructed to practice attention to daily activities (i.e., drinking, eating, walking), throughout the day; practice Body Scan exercise during the following week with aid of study CD - track 2 at least once a day; confirm next meeting

Session 5: AOB/Body Scan/Sounds

- Questions and answers related to practice in previous week (10')
- Short AOB, short body scan, followed by awareness of sounds exercise (10')
(explain what observing means: the sound, the reactions to the sound, memories, associations with the sound).
- Feedback from participant (10')

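### The three-month sexual-risk recall at the post visit reaches back before session 1, and no visit date is stated for participants withdrawn from sessions but kept in assessments

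*Combined protocol and SAP*

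**What the plan says.** - Section 8, Table 8.1 gives the post-intervention window as "Within 2 weeks of final intervention session" and the follow-up window as "12 weeks (+/- 2) after completing final intervention session". The text above the table says that these windows settle when a violation is recorded or an assessment counts as missing.
- Section 8.4 uses the same starting point in other words: "a) post-intervention (within two weeks of finishing the program) and (b) at 3 months post-intervention".
- Section 7.3 plans one session a week for 8 weeks in both arms.
- Section 6.3 says that a participant who "does not complete two intervention weeks in a row he or she may be withdrawn from the intervention portion of the study", at staff discretion, and adds: "These participants would still be contacted for pill count assessments and follow-up assessments". Section 12.7 agrees: "Withdrawals will be asked to complete follow-up assessments and home visits or phone interviews will be arranged if necessary". Neither section gives the date from which these participants' visits are counted. Nothing covers a participant who attends no session.
- Section 8.3 sets a three-month look-back for self-reported sexual behaviour. Section 8.4 reuses the baseline measures at post and follow-up and gives no other recall period.
- Section 12.3 models the outcomes at end of intervention and follow-up jointly, with condition, time and their interaction. Section 12.2 calls any formal testing exploratory.

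**The concern.** There are two separate timing problems.

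First, the recall period is longer than the time from session 1 to the post visit. Part of what a participant reports at post therefore happened before either intervention began. The arms cannot differ by intervention in those weeks, so they pull the post between-arm difference towards zero. The pilot is meant to supply preliminary effect sizes, and this one would be read too low.

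Second, the visit windows depend on an event that some participants kept in assessments never reach. If staff count from the last session attended, the two post-baseline time points in the model mean different times since session 1 according to attendance. The same visit can also be in window under one reading and out of window under another. Section 11.5 names out-of-window visits among its examples of deviations, minor or major according to circumstance, so this status has some consequence.

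**Working it through.** The plan states no figure for either point, so there is none to reproduce. The check is calendar arithmetic, with session 1 as week 0.

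**Inputs.** Weekly sessions for 8 weeks (7.3), so session 8 is at day 49 (week 7). Post is 0–14 days and follow-up 70–98 days after the final session (Table 8.1). Recall is 3 months (8.3) = 3 × 365.25/12 = 91.3 days = 13.0 weeks. Withdrawal is possible after two consecutive missed weeks (6.3).

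**1. Recall at post.** With the visit D days after session 1, the part of the recall before session 1 is 91.3 − D days, and its share is (91.3 − D)/91.3.

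| Slip in session schedule | D (days) | Recall before session 1 (weeks) | Share |
|---|---|---|---|
| none | 49–63 | 6.0–4.0 | 46–31% |
| 2 weeks | 63–77 | 4.0–2.0 | 31–16% |
| 4 weeks | 77–91 | 2.0–0.0 | 16–0% |
| 6 weeks | 91–105 | 0.0 or none | 0% |

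Assume constant event rates and an effect that starts in full at session 1. The expected count difference at post is then D/91.3 of the difference over a fully exposed recall period: 49/91.3 = 54% to 63/91.3 = 69%.

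**2. Recall at follow-up, completers.** The visit is at weeks 7 + 10 = 17 to 7 + 14 = 21. Recall starts at weeks 17 − 13 = 4 to 21 − 13 = 8, always after session 1.

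**3. Visit dates for an early stopper.** Session k is at week k − 1. If k is the last session attended, sessions k + 1 and k + 2 fall at weeks k and k + 1, so the two-missed-weeks rule can first be met at week k + 1. Counted from the last attended session, post runs from week k − 1 to k + 1 and follow-up from week k + 9 to k + 13. The post window thus closes in the week in which the rule is first met. For k = 2:

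| Date counted from | Post (weeks) | Follow-up (weeks) |
|---|---|---|
| last attended session (week 1) | 1–3 | 11–15 |
| earliest withdrawal date (week 3) | 3–5 | 13–17 |
| planned session 8 (week 7) | 7–9 | 17–21 |

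**4. Link between the points.** With follow-up at weeks 11–15, recall would start at weeks 11 − 13 = −2 to 15 − 13 = 2. For a session-2 stopper, follow-up is therefore sure to be free of pre-session recall only if the visit is timed from planned session 8.

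**The case against.** **On the visit date.** The documents do not leave three equal readings. Section 7.3 uses the final session for the one in which open awareness is taught, and the Appendix 1 overview places that exercise in session 8 only. With weekly sessions, a planned session-8 date can be computed for anyone who starts. Section 11.2 also leaves detailed data-collection procedures to a manual that is not part of these documents. This stands: the defect is a missing sentence, and the earlier dates arise only under a reading that the plan does not adopt. But no section applies the session-8 meaning to a participant who was withdrawn, and none covers a never-starter.

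**On recall.** A fixed look-back keeps the measure identical across visits. If post falls 3 months after baseline (Section 3), recall runs from baseline to post without re-counting the baseline period. The overlap is the same in both arms, and the 12.3 model already yields a separate follow-up estimate. All of this is fair. It shows that the overlap does not favour an arm. It does not remove the dilution, because the weeks between baseline and session 1 are still in the post count.

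**Stronger readings a reader might infer.**
- That the overlap affects every participant. It does so on the planned schedule, but it disappears when sessions slip by about 4 weeks (visit at the end of the window) to 6 weeks (visit on the day of the last session).
- That an early stopper's self-reports fall out of step with the pill counts. This requires tying follow-up to the last of the seven calls, which no section does. Appendix 3 also allows 21–35 days between calls, or 14–42 if necessary.
- That confirming each next meeting in Appendix 1 shows that session 8 is never scheduled. It does not: under 7.3 instructors arrange times before the intervention begins.

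**Conclusion.** Both points hold in limited form and are worth correcting.

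The recall overlap is the firmer one. On the planned schedule, 31–46% of the recall period at post precedes session 1. The shares of calendar time follow directly from the plan. The 54–69% figure also needs constant rates and an immediate, full effect, which are assumptions.

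The visit-date gap is a real omission, of uncertain effect. For a session-2 stopper the readings of follow-up differ by up to 17 − 11 = 6 weeks. The number of early stoppers is not given. The prediction in 12.2 that at least 70% of the mindfulness arm complete all sessions would still be met with up to 7 of 25 falling short (0.30 × 25 = 7.5), and not all of those need miss session 8.

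A reader might infer bias between arms. That would need differential early stopping, on which the documents say nothing, and the outcomes affected are exploratory. A reader might also infer that the primary 80% retention criterion is at risk, but 12.2 attaches no visit window to it. Nor does Section 3 contradict Table 8.1. Post at 3 months (13.0 weeks) implies a lag from baseline to session 1 of 13.0 − 9 = 4.0 to 13.0 − 7 = 6.0 weeks. Follow-up at 5 months (21.7 weeks) implies 21.7 − 21 = 0.7 to 21.7 − 17 = 4.7 weeks. Both hold at 4.0–4.7 weeks, so aligning the two is editorial.

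**What to change.** **(a) Section 12.3.** Take the self-reported sexual-risk effect size from the follow-up visit, and label the post estimate as covering partly pre-intervention time. Cost: one sentence, and the post estimate carries less weight.

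**(b) Table 8.1 and section 8.4.** State the date from which both visits are counted:
- for participants who complete session 8, its actual date, as now;
- for all other randomised participants, the actual date of session 1 plus 7 weeks;
- for those who never start, the date of the first scheduled call plus 7 weeks.

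Keep the current window widths, and allow no further shift for a delayed start, missed sessions or withdrawal. A delayed start is already contained in the actual date of session 1.

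**(c) Section 12.2.** Count any completed final follow-up visit as retained, and report the number of in-window visits separately.

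Cost of (b) and (c): a few sentences and one date rule in the tracking system, with no extra visits. Early stoppers wait longer for their visits. On the planned schedule the rule in 6.3 is first met by week 7 for anyone whose last session is the sixth or earlier (k + 1 ≤ 7), so the whole post window of weeks 7–9 remains available. If sessions have slipped before a late stop, the window may close before the stop is known. Such a visit would be reported as out of window and, at follow-up, would still count as retained.
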